Analyses will be 'per-protocol' so efficacy can be assessed, but will be restricted to children with *Ct* on their face at baseline as determined by PCR. Participants will be analysed according to the protocol they performed. Primary comparisons will be between Protocols A and B and will compare the proportion of participants without *Ct* detected on faces immediately following face washing according to each protocol. In secondary analysis we will look at *Ct* removal following Protocol C, removal of oculo-nasal discharge following Protocols A-C and mean log₁₀ reduction in load of *Ct* on faces immediately following each Protocol. A further secondary analysis will compare how quickly the load of Ct builds up on the faces of infected children, following removal by each of these four methods. Regression analyses will be performed to evaluate the relative efficacy of the various cleaning methods for removing Ct from faces using 'washing with water' as the comparison. Another secondary analysis will assess the viable load of Ct found on the SuperTowel® samples after use, to give an indication of their potential role as fomites in transmission.

We will also compare the ability of a novel, quantitative metric vs current metrics (i.e. signs of ocular and nasal discharge), to predict recent personal cleaning practices, across the four methods.

We will look for presence of Ct in stool as determined by PCR.

As ocular infection is assessed through both rapid test and PCR, we also have the opportunity to compare the results to evaluate the diagnostic ability of the rapid test.

Data management

Data from the study will be jointly managed by the LSHTM and FHF team in Ethiopia, coordinated by the Ethiopian Project Manager and the PI. Data will be entered at the time of collection via electronic data capture on password protected Android Devices using the Open Data Kit (ODK) secure data capture system provided by LSHTM http://opendatakit.lshtm.ac.uk/. All data is automatically encrypted on the Android devices when the ODK form on the Android devices is filled and finalised. The ODK Collect app uses the public encryption key along with an encryption algorithm to convert the data in to an encoded (encrypted) form. Once the form is finalised, the data cannot be reopened or

read on the device (e.g. in the case of loss or theft of the tablet). Any photographs, audio/video recordings and other attachments are also encrypted. Encrypted data will be sent over the internet from the Android devices to a secure server at LSHTM for secure storage and backup. Only the encrypted forms of the data will be stored on the servers, so no person could view any data on any server through the web, even if they have a copy of the admin username and password. In the case that WiFi is unavailable in the study area for several days, we will back up encrypted forms to the password protected laptop of the local PI.

Data will be downloaded from the ODK server and then decrypted offline using a piece of software called ODK Briefcase. This will only be done by the study investigator and co-investigators who have access to the decryption key, saved on personal usb drives kept securely in locked cabinets and offices, meaning that only a small number of individuals can ultimately see the human readable form of the data. All decrypted data containing any personal identifiers will be stored on a secure server at LSHTM and in no other place. Paper records (consent forms) will be managed and stored in the secure/locked project office in locked cabinets.

Photographs of faces will be used for independent grading by blinded assessors within the LSHTM Stronger SAFE team (not involved in the data collection for this part of the study). Photographs of each wipe will be graded off-site using computer-automated densitometry scoring.

Laboratory data will be managed through an MS Access database. The laboratory will verify the samples received from the field, noting any errors, deficiencies or missing samples. After testing, the laboratory will submit results to the PI.

The Ethiopian Project Manager and the PI will be responsible for ensuring a secure and appropriate location for storage of study related documentation present at the study site, as well as for ensuring that only members of site staff who are authorised have access to the files. The site Investigator File will be held at the project office. The Investigator File will at all times remain available for internal audits and/or inspections of regulatory authorities, including after completion of the project.

After study completion, all the relevant study documentation will be retained in accordance with the local legislation, for a minimum period of 10 years after completion of the study. Laboratory specimens will be stored indefinitely for the participants who have given consent for long-term storage of their samples. Any processing of samples after long-term storage will be subject to an assessment of the integrity and quality of the samples. In our experience over the last 20 years, ocular samples frozen at -20°C have readily detectable *Ct* DNA. The final dataset will be archived and maintained by FHF (Ethiopia) and at LSHTM.

Anonymised data sets will be made publicly available after publication, to ensure the data are available for other investigators to explore. Specific permission for this is requested in the consent form.

Data confidentiality

The data collection tools include personal identifiers (name, age and GPS location), which are used by project staff to identify participants for the purpose of follow-up. To safe guard identifiable information, all paper records will be kept in locked cabinets in the secure (locked) project office in Shashamane. Electronic data (collected via electronic data capture on password protected Android Devices using the Open Data Kit (ODK) secure data capture system provided by LSHTM http://opendatakit.lshtm.ac.uk/) will be kept in an encrypted form on password-protected computers in the project office and on a secure server at LSHTM. All decrypted data containing any personal identifiers will be stored on a secure server at LSHTM and in no other place.

Participants are asked separately whether they consent to photos being taken and they can select where and how these photos are used in reports and other communications when they provide consent. Photographs will be stored with the photo number only, not with names, ID number or identifiable data. As we will be interested in the ocular and nasal discharge present on the face, photographs will be cropped (or blurred in facial sections irrelevant to the study protocol) to focus on this element and individuals will not necessarily be recognisable from these photos.

Ethical considerations

Approval will be sought from the Federal Ministry of Innovation and Technology, the Oromia Regional Health Bureau (ORHB) Ethics Committee and the London School of Hygiene & Tropical Medicine Ethics Committee. The research will adhere to the tenets of The Declaration of Helsinki.

We will obtain written informed consent for children to take part in the study from a parent or guardian. As all participants will be younger than 12 years of age (the recommended age for assent) we will not obtain additional informed assent from our participants.

Informed consent

Prior to approaching members of the communities there will be initial dialogues with the community leaders and local health officials to introduce the purpose and nature of the research project.

Clinical screening: a large number of children will be assembled and screened by nurses for clinical signs of trachoma. This eye examination is standard and will be performed following verbal consent provided by parents/guardians.

Eye swab for rapid test (prior to study enrolment): As eye swabs will be taken from children identified during the screening to have clinical signs of trachoma, parents/guardians will be provided with information sheets and informed consent forms (Appendices 1A and 1B). Information will be provided in *Afaan Oromo*, the regional language, and will be read out loud to those unable to read. After verbal explanation of the relevant sections of the participant information sheet (Section 1. Screening) and having the opportunity to ask questions, informed consent will be gained and evidenced by a signature or thumbprint signature (deemed acceptable locally due to high rates of illiteracy), in the presence of the study team and independent witness.

Main study: Participants' parents/guardians will be again provided with information sheets and informed consent forms (Appendices 1A and 1B). Information will be provided in *Afaan Oromo*, the regional language, and will be read out loud to those unable to read. After verbal explanation of the relevant sections of the participant information sheet and having the opportunity to ask questions, informed consent will be gained and evidenced by a signature or thumbprint signature (deemed acceptable locally due to high rates of illiteracy), in the presence of the study team and independent witness.

Parents and guardians will be asked to provide consent.

The research described in this protocol does not pose risk to potential participants. Reasonable effort has been made to ensure the following:

- 1. No harm will be done.
- 2. Respect. The fundamental ethical principle will be adhered to by respecting individuals' decisions. Written Informed consent will be sought as a means to document willingness of the potential participants. No penalties whatsoever will be suffered should any potential participant refuse to participate. Further, participants will be informed that they are free to discontinue participation even without any reasons explained. Privacy will be respected at all

times; for example, if photos are taken they will be taken by family members with their full consent and the understanding that they may withdraw their consent at any time. The BMJ guidelines (British Medical Journal, 1998, 316, 1009-1011.) have been read and are adhered to.

- **3. Confidentiality.** The data collection tools include personal identifiers (name, age and GPS location), which are used by project staff to identify participants for the purpose of follow-up. To safe guard identifiable information all paper records will be kept in locked cabinets in the secure (locked) project office in Shashamane. Electronic data will be kept in an encrypted form on password protected computers in the project office and on a secure server at LSHTM.
- **4. Trained Field Workers.** All field workers will be trained in data collection and ethical considerations to ensure non-violation of ethics.
- 5. Compensation for Participants. We do not pay individuals to participate in research studies.

Treatment of trachoma

All children identified with trachoma infection will be offered Tetracycline Eye Ointment (TEO). All study participants will be treated for trachoma following the completion of Round 2. All children with clinical signs of trachoma who had a negative rapid test and were not included in the trial will be treated following screening. Mass drug administration occurs annually in these high prevalence communities, but treating again poses no harm, and is beneficial as we cannot assume all children are reached by MDA.

Safety considerations

The safety and wellbeing of the participants will be monitored and any adverse events managed/reported as appropriate.

Potential discomfort

The collection of the eye swabs might cause a few seconds of mild discomfort, but will not harm eyes in any way. The examination takes only a few moments to complete. This examination has been carried out in many countries including Ethiopia without problem. Collecting swabs from hands and faces is not uncomfortable and does not cause any pain. However, we are aware that some of the children we are collecting data from are very young and might find this experience overwhelming or very distressing.

The SuperTowel® has been developed to be an alternative to soap and water in situations where soap and water are scarce. It is like a normal cloth that you might use for cleaning, but it has been treated so that it kills many germs that land on it. The treatment is permanently bonded to the cloth, so it cannot come off on to skin, or be washed off.

While we do not envisage psychological distress resulting from any of our procedures, it is possible that participants could experience some minor psychological discomfort as a result of being questioned on their behaviour or being asked to demonstrate face washing practices for us.

Safety precautions

Eye examinations will be conducted by a fully trained ophthalmic nurse with previous experience and training with the project. Swabbing and wiping procedures will be conducted by the nurse and/or other members of the Stronger SAFE research team who have already received training in swab

collection and study methods, and have had ample practice and supervision in conducting similar protocols. Eye examinations and each swab collection takes 1-2 minutes.

We will train and sensitise our field workers to respect participants' emotions and make sure that our staff are aware that the purpose of the research is understanding and documenting behaviour; not judging participants or their families. Participants will be informed in advance that they do not need to answer any questions they are not comfortable with and they are free to stop participating at any time. We will immediately stop the study with a particular child if they show signs of undue distress.

We will use a new, clean SuperTowel® or a new bar of soap (as applicable) for every participant, so there is no risk of infection from previous people using it, and dispose of the SuperTowel® after each use, to ensure there is no potential for onward transmission. All soap used in the trial will be sourced in Ethiopia from licensed manufacturers.

In the event of minor adverse reactions such as localised skin redness and swelling or minor eye irritation, the Stronger-SAFE team field ophthalmic nurses, amongst whom [name] will be given specific extended training in adverse event management, will advise participants. A jerry can of clean water will be available in the team car at all times for rinsing the face/eyes in the event of a minor reaction. Additionally, specific medication for treating allergic reactions in the field will be available in the field medical kit to be administered by the nurses if clinically indicated.

In the case of a severe reaction such as anaphylaxis or a severe skin reaction, or should further care be required, the person will immediately be escorted to Feya hospital (the best hospital in Shashmene). The field team will always include one ophthalmic nurse who can provide interim care until the car reaches the hospital. In addition, contact with the clinicians [name] (based in Ethiopia), or the clinical team in London ([name] or [name]) will be available by telephone while fieldwork is being conducted.

Safety and field study monitoring

The Lead Investigator and the local PI will review reports of minor or serious adverse effects daily, and stop the trial immediately if any product appears to have caused a serious adverse reaction in any participant.

We will appoint an independent field study monitor, in accordance with the Guidelines issued by the Drug administration and control Authority (DACA) (formerly Ethiopian Food, Medicine and Healthcare Administration and Control Authority /EFMHACA).

The field study monitor will be responsible for observing the responsibilities of all parties and reporting to the sponsor (LSHTM). The monitor will verify that the rights and well-being of the study participants are protected, that the data are accurate, complete and verifiable from source, and that the trial is conducted in compliance with GCP and local (DACA) regulations. The field study monitor will be familiar with, and have experience with, local regulations. They will be appropriately trained and have relevant scientific knowledge to properly understand and monitor the trial.

The monitor will be thoroughly familiar with, and they will verify adherence to protocol, information and consent sheets, and SOPs (including version/document control, currently approved versions). They will verify the qualifications of the research team, enrollment of only eligible participants, correct document record keeping, production of reports, and the accuracy and completeness of the case record form.

Monitoring plan

As this is a small-scale trial that does not involve an invasive investigational product (only locally-available soap, and the use of a microfiber towel), a visiting schedule of before, during and after the clinical phase will be sufficient. The monitoring visits will be documented, and notification will immediately be given to the relevant party (i.e. co-PIs, CI, or sponsor) regarding any issue raised during these visits. A full list of the duties conducted at each of these time points is given in the table below.

Outline of monitor duties at before, during and after clinical phase visits.

Item for monitoring	Frequency			
	Before	During	After	Throughout
Communicating with investigators (PI/CI)				х
Ensuring that receipt, use and return of the SuperTowel product is				х
controlled and documented				
Ensure investigator and staff are informed about the trial so they can				x
carry out all of the processes correctly				
Verify that essential documents are properly filed and maintained				х
Verify that the investigator provides all the required reports,				x
notifications, applications and submissions, and that these documents				
are accurate, complete, timely, legible, dated, and identify the trial				
Communicating deviations from the protocol, SOP, GCP, and the				х
applicable regulatory requirements to the investigator and taking				
appropriate action designed to prevent recurrence of the detected				
deviations				
Verify that all protocol amendments are distributed to site				х
	1	I		T
Verifying that all regulatory/institutional approvals are in place prior to	Х			
IP (soap and SuperTowel products) arriving on site				
Checking that storage facilities are suitable for IP and all study materials	Х			
Checking facilities to ensure adequacy	X			
Ensure investigator receives current IB	Х			
Verifying investigator has adequate qualifications	X	Х		
Verifying that staff are adequately trained in protocol	Х	Х		
Verify that all protocol amendments are receive regulatory/institutional	Х	Х		
approval				
Ensure investigator receives all documents and supplies required to	X	Х		
conduct trial				
Verify people carrying out tasks and processes have been officially	Х	Х		
delegated these tasks				
and the second s	T	I	 	1
Monitoring suitability of facilities		Х		
Checking that participants are provided with proper instructions on IP use		X		
Verify investigator is following protocol and protocol amendments		х		
Verify that written consent has been granted prior to participants entry		х		
into the trial				
Verify the investigator recruits only eligible participants		х		
Checking the accuracy and completeness of the Case Report Form/ data		Х		
collection tool entries, source documents and other reports				
Ensuring that IP is disposed of in accordance with local		х	х	
regulations/sponsor rules				
Verify that source documents are accurate, up-to-date and maintained		Х	Х	
Informing the investigator of any errors, illegibility, omissions or		х	Х	
inconsistencies in the Case Report Form/ data collection tools				
Determining that ALL adverse events are appropriately reported		x	Х	

We will not institute an additional Data Safety Monitoring Board (DSMB) because of the low-risk nature of this behavioural trial and the fact that interventions are already readily available to the study

population. We also assume that data will accrue too quickly to make it useful for feasible for a DSMB to conduct interim analyses.

Anticipated outputs

There is currently a lot of international momentum about better understanding the 'F' component of the SAFE strategy, and there will be ample opportunity to share our findings with a broad audience. The Stronger SAFE investigator group is well placed to conduct conversations about the intervention at the right levels as it involves leaders within Ethiopia at the national and regional level, WHO and a leading implementing NGO, as well as at LSHTM. Many of the investigators are involved in the WHO GET2020 Alliance for the elimination of Trachoma.

We will inform the Ethiopian regional and Federal health authority and the community about the results via a written report and direct verbal communication. This information will be shared directly with the communities that participated in intervention development through public meetings. Formal reports will be written for the Ethiopian Federal and Regional health authority and the Federal Ministry of Science and Technology (FMOST). Reports will also be prepared for the Wellcome Trust and The Fred Hollows Foundation (Ethiopia and UK).

To ensure operational uptake of the findings of the studies, we intend to present these data at the annual National Trachoma Task Force and NTD Research Symposium (Ethiopia). Additionally, we will present this research (the process by which the intervention has been developed) at the annual Trachoma Scientific Informal Workshop prior to the WHO GET2020 Alliance meeting. Scientific results will be published in Open Access in peer-reviewed journals and presented at relevant international conferences.

Trial Sponsor

London School of Hygiene & Tropical Medicine will act as the trial sponsor. Delegated responsibilities will be assigned locally.

Audits and Inspections

The study may be subject audit by the London School of Hygiene & Tropical Medicine under their remit as sponsor, the Study Coordination Centre and other regulatory bodies to ensure adherence to GCP.

Funding

The Wellcome Trust, London, UK, is funding this study.

Indemnity

London School of Hygiene & Tropical Medicine, the trial sponsor, holds Public Liability ("negligent harm") and Clinical Trial ("non-negligent harm") insurance policies, which apply to this trial.

Trial Registration

The trial will be registered on the Pan-African Clinical Trials Registry, after it has received ethical and regulatory approval.

Appendices

- 1A Participant Information Sheet
- 1B Participant Consent Form
- 2 Data Collection Form
- 3 Swabbing SOP
- 4 SuperTowel®: Efficacy Data
- 5 SuperTowel®: Material Safety Data Sheet
- 6 Adverse Event Documentation Log
- 7 Serious Adverse Event Documentation Log

References

- 1. Taylor, H.R., et al., *Trachoma.* Lancet., 2014. **384**(9960): p. 2142-52. doi: 10.1016/S0140-6736(13)62182-0. Epub 2014 Jul 17.
- 2. *Eliminating Trachoma: Accelerating Towards 2020*. 2016, WHO Alliance for the Global Elimination of Trachoma by 2020: Geneva.

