- 4. We need new metrics of facial hygiene that are valid, reliable and useful.

Study Aim and Objectives

The primary aim is to find the optimal facial hygiene practice to reduce the likelihood of *Ct* being present on the faces of infected children in order to improve the design of interventions for trachoma control. We hypothesise face washing with soap will reduce the amount of *Ct* found on infected children's faces

Our primary objective is to assess the relative effectiveness of face washing with soap and water compared with face washing with water only on the removal of *Ct* from the faces of children with ocular trachoma infection.

Our secondary objectives are to:

- Assess the relative effectiveness of face wiping (with a product called the 'SuperTowel'®) compared with face washing with water and face washing with water and soap on removal of *Ct* from the faces of children with ocular trachoma infection.
- Assess the relative effectiveness of three facial cleanliness methods on removal of ocular and nasal discharge on the faces of children with ocular *Ct* infection
- Assess the relative effectiveness of three facial cleanliness methods on the mean reduction in *Ct* load on the faces of children with ocular trachoma infection
- Assess how long it takes for Ct to return to children's faces following face washing or wiping.
- Assess the effectiveness of the product called the 'SuperTowel'® to kill (reduce viability) of Ct transferred to it

Objectives related to the 'SuperTowel'® will be reviewed following an *in vitro* pilot to confirm the properties of the 'SuperTowel'® in relation to killing *Ct* bacteria on contact.

A further aim is to evaluate the ability of a novel, quantitative metric to predict recent personal cleaning practices. The purpose of this study is to determine whether there are meaningful differences in the sensitivities of this novel metric vs current metrics (i.e. signs of ocular and nasal discharge) to detect differences in pre- and post-cleaning facial cleanliness, across different face cleaning practices.

We are also interested in learning whether spread of *Ct* through the gastrointestinal tract might be possible.

Outcome measures

Primary outcome

• Proportion of participants without *Ct* detected on faces immediately following face washing with soap and water, compared with the face washing with water only group (i.e. To assess whether soap is needed to remove *Ct* from faces or whether water alone is sufficient).

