Secondary outcomes

- Proportion of participants without Ct detected on faces immediately following face wiping with the SuperTowel
- Proportion of participants without ocular or dry nasal discharge on faces immediately following washing/wiping protocol
- Mean log₁₀ reduction in load of Ct on faces immediately following the washing/wiping protocol
- Proportion of participants without *Ct* / ocular and nasal discharge on faces at 1, 2, 4, 6 and 8 hours following the washing/wiping protocol
- Mean log₁₀ increase in load of Ct on faces at 1, 2, 4, 6 and 8 hours following protocol
- Mean viable load of Ct found on the SuperTowel® samples after use.

The screening of such a large number of children offers an opportunity to conduct related analyses alongside our trial work. Some planned ancillary objectives are mentioned below.

- We will also compare the ability of a novel, quantitative metric vs current metrics (i.e. signs of ocular and nasal discharge), to predict recent personal cleaning practices, across the three methods.
- We will look for evidence of *Ct* in the stools of children with ocular infection, evidenced by PCR.
- We will evaluate the diagnostic ability of the rapid test used to screen for ocular infection as compared to ocular infection detected through PCR.

Methods

Study design

This is a three-arm, open, parallel-group randomised controlled trial.

Study setting and population

The study will be carried out in one *zone* in Oromia in districts with high TF prevalence in 1-9 year olds (TF1-9>40%) selected according to GTMP (Global Trachoma Mapping Project) data. We will confirm the *de facto* TF prevalence in 1-7 year olds (the eligible population for the study, see below) and the absence of recent - within the last 6 months; ideally as close to a year ago as possible -azithromycin mass drug administration (MDA) in selected *woredas* prior to commencing the study. The total population of the zone is estimated at 3.9 million . In some of the districts of this zone, trachoma surveillance survey (TSS) conducted in 2022, after five rounds of MDA, showed the TF prevalence is greater than 11% in children ages 1-9 years.

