Samples will be kept on ice-packs in the field and transferred to a -20°C freezer within eight hours. Samples will be transferred each week to the ORHB Public Health Laboratory in Adama where DNA extraction and amplification tests for *Ct* will be performed. Upon receipt in the laboratory, each sample will checked against the sample log sheets. Any missing samples or samples not suitable for analysis will be reported to the study coordinator, along with a daily report on sample submission. Samples will be stored in a -80°C freezer.

In the Adama laboratory, DNA will be extracted from the swabs and stool samples using a commercially available kit. The DNA extract will then be tested using a previously described three-plex real-time quantitative PCR assay.[29] This simultaneously tests for: (1) a human DNA target (Internal Control to confirm adequacy of sample collection, extraction and PCR reaction); (2) a *C. trachomatis* chromosomal DNA target; (3) a *C. trachomatis* plasmid DNA target. To assess the potential viability of the *Ct* detected in the non-ocular samples, we will pre-treat swab samples before extraction using PMA and light.[30]

SuperTowel®: Chlamydia trachomatis detection by quantitative PCR

SuperTowel® samples will be kept on ice-packs in the field and transferred to a -20° C freezer within eight hours. Samples will be transferred each week to the ORHB Public Health Laboratory in Adama where they are stored in a -80° C freezer. Upon receipt in the laboratory, each sample will be checked against the sample log sheets. Any missing samples will be reported to the study coordinator.

In the Adama laboratory, the SuperTowel® will be rinsed with PBS before vacuum filtration using a 0.2 micron pore diameter filter. DNA (untreated and treaded with PMA) will be extracted from the filters using a commercially available kit. The DNA extract will then be tested using the quantitative PCR assay described above. The vacuum filtration process will be piloted in the laboratory to ensure validity prior to this study.

Statistical Analysis

CONSORT guidelines for analysing and reporting clinical trials will be followed. A flowchart will show all potentially eligible and ineligible participants for the trial, and reasons for exclusion. The number of participants enrolled per protocol will be shown, along with number with outcome data. The baseline characteristics of participants will be summarised by arm.

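### The SuperTowel killing objective has only an absolute viable load as its outcome, and that cannot separate killing from low face load, poor transfer or poor recovery

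*Protocol*

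**What the plan says.** Study Aim and Objectives in the protocol lists, as a secondary objective, the effectiveness of the SuperTowel "to kill (reduce viability) of Ct transferred to it". The same section says that the SuperTowel objectives will be reviewed after an in vitro pilot, and Pilot study describes that pilot as a laboratory test of killing on contact.

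Under Secondary outcomes, the only entry on viability on the towel is "Mean viable load of Ct found on the SuperTowel" samples after use.

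Statistical Analysis repeats this quantity: "Another secondary analysis will assess the viable load of Ct found on the SuperTowel® samples after use". The reason given there is "to give an indication of their potential role as fomites in transmission".

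The laboratory section on the SuperTowel provides two readings per towel: "DNA (untreated and treaded with PMA) will be extracted from the filters using a commercially available kit". It continues: "The DNA extract will then be tested using the quantitative PCR assay described above". For non-ocular swabs, the laboratory section says "we will pre-treat swab samples before extraction using PMA and light" and mentions no untreated reading.

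**The concern.** The objective is conditional: of the Ct that reached the towel, how much lost viability? The outcome is unconditional: how much viable Ct is on the towel afterwards? The second quantity depends on how much Ct was on the face, how much the wipe picked up and how much the rinse recovered, as well as on killing. A low mean is therefore no evidence of killing.

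The face load will vary. The Sample size section expects 50% of enrolled children to have ocular infection and 60% of those to have facial Ct, so 0.5 × 0.6 = 30% of those enrolled. Restricting the analysis to children with Ct on the face at baseline removes the zeros but not the spread in load among the rest. If the objective is answered with the outcome as listed, a towel that collects little Ct and a towel that kills Ct give the same result.

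**Working it through.** The protocol gives no expected value, sample size or power for this outcome, so there is no figure to reproduce. The check is whether the outcome can identify the quantity in the objective. All numbers below are assumed for illustration, in copies.

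**Notation.** F = Ct load on the face; t = share transferred to the towel; r = share recovered in the rinse and filtration; v0 = share viable before contact; k = share of viable Ct killed by the towel.

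- Total load from the untreated extract: T = F × t × r
- Viable load from the PMA-treated extract: V = F × t × r × v0 × (1 − k)

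The objective concerns k. The listed outcome is the mean of V.

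**Step 1: the simplest case.** With r = v0 = 1, V = transferred × (1 − k). Then 100 × 1 = 100; 10,000 × 0.01 = 100; 100,000 × 0.001 = 100. Kills of 0%, 99% and 99.9% give the same outcome value.

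**Step 2: which factor produces the low value.** Four situations, all with v0 = 1:

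| Situation | F | t | r | k | V | T | V/T |
|---|---|---|---|---|---|---|---|
| Good transfer, 90% killed | 10,000 | 0.90 | 1 | 0.90 | 900 | 9,000 | 0.10 |
| Poor transfer, none killed | 10,000 | 0.09 | 1 | 0 | 900 | 900 | 1.00 |
| Low face load, none killed | 1,000 | 0.90 | 1 | 0 | 900 | 900 | 1.00 |
| Poor recovery, none killed | 10,000 | 0.90 | 0.10 | 0 | 900 | 900 | 1.00 |

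The outcome V is 900 in every row. The ratio V/T separates the first row from the other three.

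**Step 3: what the ratio removes.** V/T = v0 × (1 − k). F and t cancel. r cancels only if viable and non-viable organisms are recovered equally well.

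**Step 4: what the ratio leaves.**

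- *Viability before contact.* F = 10,000, t = 0.90, r = 1, v0 = 0.10, k = 0 gives V = 900, T = 9,000 and V/T = 0.10, the same as the first row with no killing at all.
- *Storage.* Towels are kept on ice packs, frozen at −20°C and then at −80°C before the rinse. Viability lost there lowers V/T just as killing does.
- *Filtration.* About the SuperTowel describes killing by membrane disruption with leakage of cell contents, and the laboratory section recovers material on a 0.2 micron filter. DNA from lysed cells may pass through. In the first row, 900 organisms are viable and 8,100 killed. If half the DNA of the killed organisms were lost, T = 900 + 4,050 = 4,950 and V/T = 900 / 4,950 = 0.18. If all were lost, T = 900 and V/T = 1.00. This error understates killing, whereas prior non-viability and storage loss overstate it.

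**Step 5: non-detects.** If no viable Ct is detected, log10(V/T) is undefined. Such a towel shows only that V lies below the assay limit L, so its ratio lies below L/T. Dropping these towels would remove the ones with the strongest apparent effect.

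**The case against.** The strongest reply is that killing is assigned elsewhere. The in vitro pilot tests it directly, the field objective is provisional until that pilot is reviewed, and the field measurement has its own stated purpose, the fomite question, for which absolute viable load is the right quantity. Combining two planned readings into a derived variable could also be left to a statistical analysis plan that is not shown. And the ratio is not a clean measure of killing either.

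Part of this stands. The fomite outcome is sound and should stay, and the limits of the ratio are real. But the killing objective is in the current text alongside the outcome that is meant to serve it. The pilot may change the objective later; it does not change the listed outcome now. The protocol itself names that outcome, so this is a mismatch already fixed rather than a detail left open. The ratio's remaining faults also affect absolute viable load when it is read as killing, and that measure carries face load and transfer as well.

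A reader might infer three stronger points. None is supported:

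- *That the trial will report a poorly collecting towel as an effective killer.* The protocol nowhere says that a low viable load will be read as killing, and the untreated reading means total load will be known.
- *That the two planned towel readings are enough to prove killing.* Step 4 of the working shows that they are not.
- *That the child's baseline face swab is a ready comparator.* An untreated reading of the swabs is not stated. Swabs go into 2SP medium while towels may go into a sealed bag, so a difference could reflect storage.

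**Conclusion.** The concern holds as a mismatch between one secondary objective and its only outcome. Mean viable load on used towels answers the fomite question; it does not identify how much of the transferred Ct was killed. That conclusion is algebraic and does not depend on the assumed copy numbers, which show that kills from 0% to 99.9% can share one outcome value but say nothing about the size of the problem in this trial.

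A viable-to-total ratio from readings already planned is a better measure because face load and transfer cancel. It still rests on three things that the protocol does not establish: viability before contact, stability in storage, and equal recovery of DNA from intact and lysed organisms. Without a comparator it supports a statement about the viable share of Ct recovered from used towels, not about killing by the towel. The primary comparison of soap and water with water only is untouched.

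**What to change.** - Keep mean viable load on used towels as the outcome for the fomite question.
- For the killing objective, report total (untreated) and viable (PMA-treated) load together for each towel, with the within-towel log10 ratio of viable to total load, in towels with Ct detected in the untreated extract.
- Treat PMA-treated non-detects as left-censored at the assay limit, and report how many there are.
- State that the ratio removes face load and transfer but does not alone attribute lost viability to the towel, for the three reasons in the working. Word the result as the viable share of Ct recovered from used towels, read alongside the in vitro pilot.
- If the ratio is not adopted, reword the objective to viable contamination of the towel after use. The review planned after the pilot is a natural time for either change.

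The cost is a few lines of outcome and analysis text, with no new arm and no new towel sample or assay. A baseline face-swab ratio is optional only: it would need an untreated extraction and PCR where none is stated, and differences in storage would limit what it shows.
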